## NON-INTERVENTIONAL (NI) STUDY PROTOCOL

### Study information

Title	Hospital Readmissions Among Nonvalvular Atrial Fibrillation Patients Treated with Oral Anticoagulants in the U.S.
Protocol number	B0661122
Protocol version identifier	1
Date of last version of protocol	July 12, 2018
EU Post Authorisation Study (PASS) Register Number	
Medicinal Product	Apixaban
Research question and objectives	
Primary research question: What is the frequency of readmission for major bleeding (MB) within 1 month after an index hospitalization for nonvalvular atrial fibrillation (NVAF) patients treated with apixaban, dabigatran, rivaroxaban, or warfarin?
 
Primary objective:
 
 
• To evaluate and compare 1-month MB-related readmission rates of hospitalized NVAF patients treated with dabigatran, rivaroxaban, or warfarin vs. apixaban
 
 
Secondary objectives:
 
 
○ To evaluate and compare 1-month all-cause readmission rates of hospitalized NVAF patients treated with dabigatran, rivaroxaban, or warfarin vs. apixaban
 
○ To determine average hospital length of stay (LOS) and costs associated with MB-related and all-cause readmissions occurring within 1 month of initial hospitalizations of hospitalized NVAF patients treated with dabigatran, rivaroxaban, or warfarin vs. apixaban
 
 
Exploratory objectives:

	

• To describe 1-month stroke-related readmission rates of hospitalized NVAF patients treated with dabigatran, rivaroxaban, or warfarin vs. apixaban

• To describe average hospital LOS and costs associated with stroke-related readmissions occurring within 1 month of initial hospitalizations of hospitalized NVAF of patients treated with dabigatran, rivaroxaban, or warfarin vs. apixaban

• To describe readmission rates, hospital LOS and costs associated with all-cause, MB-related and stroke-related readmissions occurring within 3 months of initial hospitalizations of hospitalized NVAF of patients treated with dabigatran, rivaroxaban, or warfarin vs. apixaban

Authors	[name], MBA [contact] Email : [contact]  [name], JD, MPH [contact] Email: [contact]

## 1. LIST OF ABBREVIATIONS

Abbreviation	Definition
AF	Atrial Fibrillation
AFL	Atrial Flutter
CCI	Charlson Comorbidity Index
CHADS 2	Congestive heart failure, Hypertension, Age $\geq$ 75 years, Diabetes mellitus, Stroke
CHADS 2 -VASc	Congestive heart failure, Hypertension, Age $\geq$ 75 years, Diabetes mellitus, Stroke, Vascular disease, Age 65-74 years, Sex category
DOAC	Direct-acting Oral Anticoagulant
HAS-BLED	Hypertension, Abnormal Renal/Liver Function, Stroke, Bleeding History or Predisposition, Labile International Normalized Ratios, Elderly, Drugs/Alcohol
HIPAA	Health Insurance Portability and Accountability Act
ICD-9 CM	International Classification of Diseases, 9th Revision
ICD-10 CM	International Classification of Diseases, 10th Revision
MB	Major Bleeding
NVAF	Nonvalvular Atrial Fibrillation
OAC	Oral Anticoagulant
PSM	Propensity Score Matching

### 3. ABSTRACT

**Title:** Hospital Readmissions Among Nonvalvular Atrial Fibrillation Patients Treated with Oral Anticoagulants in the U.S.

**Version:** 1

**Date of Protocol:** March 26, 2018

**Author:** [name], MBA, Novosys Health; [name], JD, MPH, Pfizer

**Rationale and background:** Hospital readmission rates are a critical concern in the U.S. and in October of 2012 the Hospital Readmissions Reduction Program was implemented by the Centers for Medicare and Medicaid Services (CMS) to reduce the frequency of readmission among Medicare patients. It has therefore become increasingly important to examine hospital readmission rates and the factors associated with readmission. Although, readmission rates of NVAF patients have been studied to some extent in regard to all-cause readmissions, little information exists in the published literature on bleeding-related readmissions. We previously conducted an early evaluation that investigated rates of all-cause and bleeding-related readmissions among NVAF patients treated with dabigatran, rivaroxaban, and apixaban (January 1, 2012 through March 31, 2014). This current analysis will be a follow-up of our earlier assessment and will include in addition to NVAF patients treated with DOACs, patients treated with warfarin. Patients hospitalized for NVAF and treated with OACs will be identified from January 1, 2013 through June 30, 2017.

**Research question:** What is the frequency of readmission for major bleeding (MB) within 1 month after an index hospitalization for nonvalvular atrial fibrillation (NVAF) for patients treated with apixaban, dabigatran, rivaroxaban, or warfarin?

Note: we anticipate that the sample size of patients treated with edoxaban is low and thus do not include edoxaban in this study evaluation. This is consistent with previous alliance NVAF studies.

#### **Objectives:**

##### Primary objective:

- To evaluate and compare 1-month MB-related readmission rates of hospitalized NVAF patients treated with dabigatran, rivaroxaban, or warfarin vs. apixaban

##### Secondary objectives:

- To evaluate and compare 1-month all-cause readmission rates of hospitalized NVAF patients treated with dabigatran, rivaroxaban, or warfarin vs. apixaban
- To determine average hospital length of stay (LOS) and costs associated with MB-related and all-cause readmissions occurring within 1 month of initial hospitalizations of hospitalized NVAF patients treated with dabigatran, rivaroxaban, or warfarin vs. apixaban

Exploratory objectives:

- To describe 1-month stroke-related readmission rates of hospitalized NVAF patients treated with dabigatran, rivaroxaban, or warfarin vs. apixaban
- To describe average hospital LOS and costs associated with stroke-related readmissions occurring within 1 month of initial hospitalizations of hospitalized NVAF of patients treated with dabigatran, rivaroxaban, or warfarin vs. apixaban
- To describe readmission rates, hospital LOS and costs associated with all-cause, MB-related and stroke-related readmissions occurring within 3 months of initial hospitalizations of hospitalized NVAF of patients treated with dabigatran, rivaroxaban, or warfarin vs. apixaban

**Study design:** The study will be a retrospective cohort analysis using the Premier Hospital database. The overall study period will be from January 1, 2012 through September 30, 2017, to allow for a 1-month follow-up period for observation of readmissions.

**Population:** Adult patients (age  $\geq 18$  years) hospitalized for NVAF, based on a primary or secondary discharge diagnosis code indicating NVAF, will be identified from the Premier Hospital database between January 1, 2013 and June 30, 2017. Patients who received apixaban, dabigatran, rivaroxaban, or warfarin during any time of the hospitalization (from admission to discharge) will be identified and grouped into study cohorts based on the oral anticoagulant (OAC) initiated. The first of such NVAF hospitalizations will be defined as the index hospitalization. Patients with more than one type of OAC drug usage during the index hospitalizations will be excluded so that patients can be exclusively assigned into each of the OAC patient cohorts.

**Variables:** Demographic, patient clinical characteristics, hospital characteristics, and key anticoagulant treatment-related information will be measured during the index hospitalization of NVAF patients. Other clinical characteristics (e.g. prior bleeding) of NVAF patients will be measured during a 12-month baseline period. The proportions of patients treated with apixaban, dabigatran, rivaroxaban, and warfarin that have MB-related, all-cause, and stroke-related readmissions that occur within 1 month of discharge of their initial hospitalization for NVAF will be evaluated. Hospital LOS and associated costs of MB-related and all-cause readmissions will be determined and compared between the other OAC cohorts and the apixaban cohort. Hospital cost data from the Premier database will reflect the hospital perspective (cost occurred to hospitals). Hospital LOS and associated costs of stroke-related readmissions will be evaluated by descriptive statistics as an exploratory analysis. Readmission rates, hospital LOS and costs associated with all-cause, MB-related and stroke-related readmissions occurring within 3 months of initial hospitalizations of hospitalized NVAF of patients will be evaluated by descriptive statistics as an exploratory analysis.

**Data sources:** The study will be conducted using the Premier Hospital database which is a nationally representative inpatient hospitalization records database that captures more than 45 million hospital discharges from greater than 600 acute care hospitals, representing approximately 20% of all hospital admissions in the U.S.

**Study size:** The preliminary data evaluation of the Premier database indicated that there are at least 30,000 patients for each of OAC cohort during the study period described for this study. With a two-sided test, an alpha-level of 0.05, and a 1:1 ratio of the comparison cohorts, and the assumed one-month MB-related readmission rate of 1.4%, and the assumed MB-related readmission rate difference of 0.5% between cohorts treated with other OACs vs. apixaban, we have estimated the following power calculation.

Power Calculation		
Nominal Power	Actual Power	N Total-One Arm
0.7	0.7	11,226
0.75	0.75	12,622
0.8	0.8	14,274
0.85	0.85	16,328
0.9	0.9	19,108
0.95	0.95	23,630

Thus, the study is expected to have sufficient sample sizes for the study measurements.

**Data analysis:** Means  $\pm$  standard deviations, and medians will be provided for continuous variables. Numbers and percentages will be provided for dichotomous and polychotomous variables. Bivariate comparisons of baseline patient and hospital characteristics and readmission measurements will be provided, with appropriate tests (e.g., ANOVA test, chi-square test) used based on the distribution of the measure. A propensity score matching (PSM) 1:1 technique will be used to control for confounders when comparing each of the OAC cohorts vs. the apixaban cohort. A logistic regression analysis will be carried out on the matched patient cohorts to further evaluate the potential impact of treatment with the different OACs vs. treatment with apixaban on 1-month MB-related and all-cause readmissions. Only the index drug will be the covariate, since other patient characteristics are expected to be similar already after the PSM. Since the patient sample size attribution in the PSM process is not known, if the population sizes are not sufficient after the PSM attrition, a multivariable logistic regression analysis will be carried out to assess the potential impact of treatment with the different OACs compared to treatment with apixaban on 1-month MB-related and all-cause readmissions, separately. The independent covariates in the regression analyses will include key patient demographics and hospital characteristics. The final list of such covariates will be determined with inputs from the Pfizer team. Additionally, we will carry out a two-part model analysis and a generalized linear model with log transformation and gamma distribution to examine the impact of treatment with the 3 different OACs vs. apixaban on MB-related and all-cause hospital readmission costs. Measurements related to exploratory objectives will be analyzed using descriptive statistics. All data analysis will be executed using statistical software SAS version 9.4.

**Milestones:**

Milestone	Planned date
Draft study protocol	April 6, 2018
Final study protocol	
Registration in the EU PAS register	
Start of data analysis	
End of data analysis	
Final study report	

#### 4. AMENDMENTS AND UPDATES

Amendment number	Date	Substantial or administrative amendment	Protocol section(s) changed	Summary of amendment(s)	Reason

## 5. MILESTONES

Milestone	Planned date
Draft study protocol	April 6, 2018
Final study protocol	
Registration in the EU PAS register	
Start of data analysis	
End of data analysis	
Final study report	

## 6. RATIONALE AND BACKGROUND

Atrial fibrillation (AF) is a cardiac rhythm disorder that is predominately nonvalvular (NVAF). It becomes increasingly more prevalent as people age and is associated with up to a 5-fold higher stroke risk in the U.S. Taking into consideration the growing elderly population in the U.S., the number of persons with NVAF is estimated to double or possibly triple by 2050. Consequently, the economic burden of NVAF, largely related to hospitalizations, is also predicted to increase from an estimated \$13.9 billion annually in 2010 to nearly \$30 billion annually by 2050.

Patients with NVAF have been reported to have high rates of hospital readmission. A retrospective database analysis of 8,035 AF and AF flutter (AFL) patients between 2007 and 2008 reported that 38% of AF/AFL patients were readmitted to the hospital for all causes within 12 months after discharge, with the highest proportion occurring within the first 1 month after discharge. This study also found that readmissions for AF and AFL had longer hospital stays and were more costly than the initial hospitalizations. A second study of 6,439 NVAF patients reported an all-cause 1-month readmission rate of 18% and that predictors of readmission included longer initial hospital length of stay, higher Charlson Comorbidity Index score, and hospital admission via the emergency room.

Hospital readmission rates are a critical concern in the U.S. and in October of 2012 the Hospital Readmissions Reduction Program was implemented by the Centers for Medicare and Medicaid Services (CMS) to reduce the frequency of readmission among Medicare patients. This program involves assigning financial penalties to hospitals with readmission rates considered excessive. In 2013, CMS reported that two-thirds of hospitals in the U.S. received penalties totaling ~\$280 million and these penalties are expected to increase in the upcoming years. It has therefore become increasingly important to examine hospital readmission rates and the factors associated with readmission. Although, readmission rates of NVAF patients have been studied to some extent in regard to all cause readmissions (most

recent patient data from 2007 to 2008), little information exists in the published literature on bleeding-related readmissions. In the real-world setting bleeding is a significant burden healthwise and economic wise and represents a critical target for improving the quality of care of NVAF patients. In clinical trials NVAF patients treated with the different DOACs differed in bleeding rates and the DOACs with lower bleeding risk have potentially a greater likelihood of improving the anticoagulation management of NVAF patients in the real-world setting where bleeding rates are higher than observed in the clinical trial setting. We previously conducted an early evaluation that investigated rates of all-cause and bleeding-related hospital readmissions among NVAF patients treated with dabigatran, rivaroxaban, and apixaban (January 1, 2012 through March 31, 2014). In this early analysis of 74,730 patients identified from the Premier Hospital database, after controlling for differences in patient characteristics, compared with patients who received apixaban during their index hospitalizations, the odds of bleeding-related hospital readmissions were significantly greater by 1.4-fold ( $p < 0.01$ ) for patients who received rivaroxaban and 1.2-fold ( $p = 0.16$ ) numerically trending greater for patients who received dabigatran. This current analysis will be a follow-up of our earlier assessment and will include patients treated with warfarin in addition to NVAF patients treated with DOACs. Recent real-world evidence has suggested that unmeasured or unmeasurable secular trends in prescribing patterns may contribute to differential outcomes observed with DOACs. For this study, patients hospitalized for NVAF and treated with OACs will be identified from January 1, 2013 through June 30, 2017, a time period in which dabigatran, rivaroxaban, and apixaban were all available, and 1- and 3-month readmission outcomes will be evaluated.

This non-interventional study is designated as a Post-Authorisation Safety Study (PASS) and is conducted voluntarily by Pfizer.

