- Had medical claims indicating a hip or knee replacement surgery during the index hospitalizations or within a 6-week period prior to the index date
  1. ICD-9 diagnosis codes V43.64 and V43.65
  2. ICD-10 diagnosis codes Z96.64x and Z96.65x
  3. ICD-9 procedure codes 81.40, 81.51, 81.52, 81.53, 81.54, and 81.55
  4. ICD-10 procedure codes 0SQ9x, 0SQBx, 0SR9019-0SR904Z, 0SR907Z, 0SR90Jz, 0SR90KZ, 0SRAx, 0SRB019-0SRB04Z, 0SRB07Z, 0SRB0Jx, 0SRB0KZ, 0SRC07Z, 0SRC0Jx, 0SRC0KZ, 0SRC0Lx, 0SRD07Z, 0SRD0Jx, 0SRD0KZ, 0SRD0Lx, 0SREx, 0SRRx-0SRWx, 0SW90JZ, 0SW93JZ, 0SW94JZ, 0SWA0JZ, 0SWA3JZ, 0SWA4JZ, 0SWB0JZ, 0SWB3JZ, 0SWB4JZ, 0SWC0JC, 0SWC0JZ, 0SWC3JC, 0SWC3JZ, 0SWC4JC, 0SWC4JZ, 0SWD0JC, 0SWD0JZ, 0SWD3JC, 0SWD3JZ, 0SWD4JC, 0SWD4JZ, 0SWE0JZ, 0SWE3JZ, 0SWE4JZ, 0SWR0JZ, 0SWR3JZ, 0SWR4JZ, 0SWS0JZ, 0SWS3JZ, 0SWS4JZ, 0SWT0JZ, 0SWT3JZ, 0SWT4JZ, 0SWU0JZ, 0SWU3JZ, 0SWU4JZ, 0SWV0JZ, 0SWV3JZ, 0SWV4JZ, 0SWW0JZ, 0SWW3JZ, and 0SWW4JZ.
- Had medical claims indicating pregnancy at any time during the study period
  1. ICD-9 diagnosis codes 630-679, V22, V23, V24, V27, V28, V61.6, V61.7, 792.3, and 796.5
  2. ICD-10 diagnosis codes A34, O00.00-O9A.53, Z33.1-Z37.9, Z39.x, and Z64.0
  3. ICD-9 procedure codes 72-75.9
  4. ICD-10 procedure codes 0DQPx-0DQQ8ZZ, 0DQRx, 0JCBx, 0Q82x, 0Q83x, 0TQBx, 0TQDx, 0U7C7ZZ, 0UCG0ZZ, 0UCG3ZZ, 0UCG4ZZ, 0UCM0ZZ, 0UJD7ZZ, 0UQ9x, 0UQCx, 0UQGx, 0UQMx, 0US90ZZ, 0US94ZZ, 0US9XZZ, 0W3Rx, 0W8NXZZ, 0WQNXZZ, 109x, 10A00ZZ, 10A03ZZ, 10A04ZZ, 10A07Z6, 10A07ZX, 10A07ZZ, 10A08ZZ, 10D0x, 10D1xZZ, 10Ex-10S0x, 10T20ZZ-10T24ZZ, 10Yx, 2Y44X5Z, 3027x, 3E030VJ, 3E033VJ, 3E040VJ, 3E043VJ, 3E050VJ, 3E053VJ, 3E060VJ, 3E063VJ, 3E0DXGC, 3E0E305-3E0E3TZ, 3E0E705, 3E0E729-3E0E7TZ, 3E0E805, 3E0E829-3E0E8TZ, 3E0P7GC, 4A0Hx, 4A0Jx, 4A1Hx, and 4A1Jx
- Received edoxaban during the index hospitalization or within 12 months prior to the index date
- Received multiple types of OACs during the index hospitalization

- Patients who died during the index hospitalizations

All the ICD-10 codes corresponding to the ICD-9 codes listed above will also be used to identify the conditions and procedures in the inclusion and exclusion criteria.

These inclusion and exclusion criteria are aligned with the Eliquis Harmonized Retrospective Study Protocol and are consistent with other previous apixaban retrospective database studies of patients with NVAf.

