**Table 1. Demographic Variables, Patient Clinical Characteristic Variables, and Hospital Characteristic Variables**

Variable	Role	Operational definition
Age	Patient characteristic and potential confounder	Age will be defined as of the index date and used to assign patients to age groups: 18-34, 35-44, 45-54, 55-64, 65-74 and >75 years, evaluated on the index date.
Gender	Patient characteristic and potential confounder	Distribution of female and male patients and reported as count and percentage, evaluated on the index date.
Race	Patient characteristic and potential confounder	Patients with White, Black, and other/unknown race and reported as count and percentages, evaluated on the index date.
Payer Type	Patient characteristic and potential confounder	Patients with Medicare, Medicaid, commercial, and other/unknown insurance coverage and reported as counts and percentages, evaluated on the index date.
Index Hospitalization Deyo-Charlson Comorbidity Index	Patient characteristic and potential confounder	The Deyo-Charlson Comorbidity Index will be calculated for the index hospitalization .

Variable	Role	Operational definition
Baseline CHADS2	Patient characteristic and potential confounder	The CHADS 2 score evaluated from the available records of the index hospitalization and baseline period will be used to estimate stroke risk. The maximum score is 6. CHADS 2 scores: 0, 1,2, ≥3
Baseline CHADS2-VASc Score	Patient characteristic and potential confounder	The CHADS 2 VASc score evaluated from the available records of the index hospitalization and baseline period will be used to estimate stroke risk. The maximum score is 9. CHADS 2 -VASc scores: 0, 1,2, ≥3
Baseline HAS-BLED Score	Patient characteristic and potential confounder	HAS-BLED score evaluated from the available records of the index hospitalization and baseline period will be used to estimate the risk of MB for patients.
Baseline Prior Bleed	Patient characteristic and potential confounder	Patients with a bleeding diagnosis on hospital records during the baseline period and reported as count and percentage. Bleeding diagnosis will have a breakdown of any, gastrointestinal, and intracranial.

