### 8.7. Data analysis

Means  $\pm$  standard deviations, and medians will be provided for continuous variables. Numbers and percentages will be provided for dichotomous and polychotomous variables. Bivariate comparisons of baseline patient and hospital characteristics and readmission measurements will be provided, with appropriate tests (e.g., ANOVA test, chi-square test) used based on the distribution of the measure. A propensity score matching (PSM) 1:1 technique will be used to control for confounders when comparing each of the OAC cohorts vs. the apixaban cohort. A logistic regression analysis will be carried out on the matched patient cohorts to further evaluate the potential impact of treatment with the different OACs vs. treatment with apixaban on 1-month MB-related and all-cause readmissions. Only the index drug will be the covariate, since other patient characteristics are expected to be similar already after the PSM. Since the patient sample size attribution in the PSM process is not known, if the population sizes are not sufficient after the PSM attrition, a multivariable logistic regression analysis will be carried out to assess the potential impact of treatment with the different OACs compared to treatment with apixaban on 1-month MB-related and all-

cause readmissions, separately. The independent covariates in the regression analyses will include key patient demographics and hospital characteristics. The final list of such covariates will be determined with inputs from the Pfizer team. Additionally, we will carry out a two-part model analysis and a generalized linear model with log transformation and gamma distribution to examine the impact of treatment with the 3 different OACs vs. apixaban on MB-related and all-cause hospital readmission costs. Measurements related to exploratory objectives will be analyzed using descriptive statistics. All data analysis will be executed using statistical software SAS version 9.4.

Detailed methodology for summary and statistical analyses of data collected in this study will be documented in a Statistical Analysis Plan (SAP), which will be dated, filed and maintained by the sponsor. The SAP may modify the plans outlined in the protocol; any major modifications of primary endpoint definitions or their analyses would be reflected in a protocol amendment.

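### Section 6 raises secular prescribing trends, but no listed confounder or named model term carries calendar time, so drug and index date may stay confounded

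*Protocol*

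**What the plan says.** Section 6 of the protocol states that "unmeasured or unmeasurable secular trends in prescribing patterns may contribute to differential outcomes observed with DOACs". It then sets the identification period: patients "will be identified from January 1, 2013 through June 30, 2017", described as "a time period in which dabigatran, rivaroxaban, and apixaban were all available". No other measure against secular trends is given, and section 8.9 does not list them as a limitation.

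For confounding, section 8.7 says that "A propensity score matching (PSM) 1:1 technique will be used to control for confounders" in each comparison with apixaban. It does not itemise the propensity-score covariates. Table 1 gives each of its variables the role "Patient characteristic and potential confounder". They run from age, gender, race and payer through comorbidity and risk scores, prior events, dose strength and other anticoagulants to hospital region, urban or rural status, teaching status and bed size. None is a calendar-time variable.

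The outcome model after matching is fixed: "Only the index drug will be the covariate, since other patient characteristics are expected to be similar already after the PSM". If matching leaves too few patients, section 8.7 substitutes a multivariable logistic regression on demographics and hospital characteristics, with the final covariate list still to be settled.

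**The concern.** That all three DOACs could be prescribed throughout the window does not mean that each was prescribed at the same pace throughout it. Over four and a half years one drug's patients may cluster late and another's early, and a match on Table 1 alone can pair an apixaban patient with a comparator patient discharged years before. The window is defined by DOAC availability, so it offers no balance of dates for warfarin either.

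The reason given for a drug-only outcome model is that matching will already have made patients similar. That reasoning reaches only what is matched on, and index date is not a listed characteristic.

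The protocol itself suggests one route by which outcomes could drift: section 6 describes readmission penalties that began in October 2012 and were expected to grow. If outcomes drifted and uptake differed, part of the drift would appear as a drug effect in the primary major-bleeding (MB) contrast, in all-cause readmission or in costs.

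**Working it through.** **1. The protocol's own figure, for scale.** Inputs from section 8.5 and Table 3: rate 1.4%, difference 0.5 points, two-sided alpha 0.05, 1:1. Taking 1.4% against 0.9%, with mean rate 0.0115:

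- n per arm = [1.960·√(2·0.0115·0.9885) + 0.842·√(0.014·0.986 + 0.009·0.991)]² / 0.005² = 7,137.
- Both arms: 2 × 7,137 = 14,274, the Table 3 entry at 80% power. The design contrast is thus a ratio of 1.4/0.9 = 1.56.
- With the 30,000 patients per cohort quoted in section 8.5, power for this contrast exceeds 99.9%, so fairly small differences can reach significance.

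**2. Where calendar time could enter the analysis.**

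| Step | What the protocol names | Calendar time? |
|---|---|---|
| Index window (section 6) | Period with all three DOACs available | Restricts the range; does not balance within it |
| Table 1 | Patient, clinical and hospital variables | No |
| Post-match model (8.7) | Index drug only | No |
| Fallback regression (8.7) | Demographics and hospital characteristics, list open | Not named |

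The window is 54 months (January 2013 to June 2017). The inclusion criteria in section 8.2.1 give September 30, 2017 as the end, which would make it 57. The point is the same either way.

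**3. Size of a spurious ratio under assumed inputs.** The protocol gives neither uptake by year nor outcome rates by year, so everything here is assumption. Split the window into an earlier and a later era. Let pa and pc be the later-era shares of apixaban and comparator patients, and r the later rate divided by the earlier rate. Assume no drug effect, and that matching on Table 1 leaves the era shares unchanged. The apparent comparator-to-apixaban ratio is

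[(1 − pc) + pc·r] / [(1 − pa) + pa·r]

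- pa = 0.6, pc = 0.3, r = 0.8: 0.94/0.88 = 1.07.
- pa = 0.6, pc = 0.3, r = 1.2: 1.06/1.12 = 0.95.
- pa = 0.5, pc = 0.4, r = 0.8: 0.92/0.90 = 1.02.
- pa = 0.5, pc = 0.4, r = 1.2: 1.08/1.10 = 0.98.
- pa = pc, or r = 1: exactly 1.

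**4. Consequence for a false positive.** Take the 1.07 case with a 1.4% comparator rate and 30,000 per arm, ignoring matching loss. Apixaban would show 1.4%/1.068 = 1.31%, a difference of 0.09 points. The standard error is √[(0.014·0.986 + 0.0131·0.9869)/30,000] ≈ 0.094 points, so the shift is about 0.94 standard errors. The chance of a significant result against the comparator rises from 2.5% to about 15%.

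Other assumed inputs, also with no drug effect and 30,000 per arm:

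| Early / late MB rate | Early share, apixaban vs comparator | Spurious difference | Odds ratio | Chance of significance against comparator |
|---|---|---|---|---|
| 1.9% / 1.4% | 20% vs 60% | 0.20 points | 1.14 | about 50% |
| 1.6% / 1.4% | 20% vs 60% | 0.08 points | 1.06 | about 12% |
| 1.5% / 1.4% | 40% vs 50% | 0.01 points | 1.01 | about 3% |
| 1.4% / 1.4% | any | 0 | 1.00 | 2.5% |

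**5. Cost of exact matching on era.** With equal cohort sizes, the largest share of patients that can be paired is min(pa, pc) + min(1 − pa, 1 − pc).

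- 60% vs 30% later-era: 0.30 + 0.40 = 70%, a loss of up to 30% of pairs.
- 50% vs 40%: 0.40 + 0.50 = 90%, a loss of 10%.

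**The case against.** The strongest reply is that the propensity-score covariates are nowhere listed. Table 1 is headed as a table of demographic, clinical and hospital variables and is not declared exhaustive. Section 8.7 defers detailed methods to a statistical analysis plan that is not at hand and that could add index year. This stands as a limit on certainty: that calendar time is absent from the match is an inference from Table 1. It does not remove the point. The protocol itself fixes a table of potential confounders, a drug-only outcome model and the covariate classes of the fallback, and a confounder suggested by its own rationale is in none of them.

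A second reply is that the bias is hypothetical and mostly small. A ratio of 1.07 is minor beside the design contrast of 1.56 or the 1.4-fold odds that section 6 reports for rivaroxaban in the earlier evaluation. That is fair, although 1.07 is about a third of the excess in the 1.2-fold odds reported there for dabigatran.

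Three stronger readings are tempting, and the documents do not support them.

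- A reader might infer that the protocol admits secular trends create false differences between DOACs. It says only that they may contribute.
- A reader might infer that drug and era are certainly confounded. That needs both differing uptake and an outcome trend, and neither is reported.
- A reader might infer that the mix of ICD-9 and ICD-10 makes bleeding and comorbidity ascertainment differ by era. The sentence "All the ICD-10 codes corresponding to the ICD-9 codes listed above will also be used" concerns eligibility codes only. The changeover date is not stated, and the outcome code list in Annex 2 is not available in the text reviewed. A coding effect is possible but not shown.

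**Conclusion.** The point holds in a limited form. The protocol raises secular trends, answers them with a window that restricts index dates without balancing them, and names calendar time in no confounder list or model. Followed as written, the analysis would leave index date unbalanced wherever uptake differed between drugs.

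Whether that biases the results cannot be settled from the protocol. Under the two-era assumptions in step 3, the spurious ratio runs from none to about 1.07, or 0.95 in the other direction. Steeper assumed trends and uptake differences give more (an odds ratio of 1.14 in the widest case tried), and equal uptake or a flat rate gives nothing. These are illustrations, not estimates. The gap is worth closing because the cohorts are large enough for a modest bias to reach significance, and because the alternative explanation is one that the protocol itself puts forward.

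**What to change.** Add index calendar year or quarter to Table 1 as a potential confounder. Include it in each of the three pairwise propensity scores, in the fallback regression and in the cost models, and report balance by index year after matching alongside the other covariates. If the statistical analysis plan already does this, the protocol should say so.

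Exact matching on index year or coding era can be a sensitivity analysis, with the era boundary defined in the document.

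The index date is already defined in section 8.2 as the discharge date, so no new data are needed. As a propensity-score term, the cost should be a small number of additional unmatched patients. Exact matching on era is dearer: up to about 10% to 30% of pairs under the assumed shares and equal cohort sizes, and possibly more for exact matching on year. At 30,000 per cohort, a 30% loss from this source alone would leave 21,000 per arm, against the 7,137 per arm that reproduces the Table 3 entry for 80% power.
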